4.1 Objectives

To determine whether breaking up sitting time with standing or light physical activity acutely improves cardiometabolic risk markers and cardiac function in individuals who have suffered a myocardial infarction.

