4.2 Outcome

The primary outcome of this study is postprandial glucose. Other outcome measures include: (i) cardiometabolic risk markers: postprandial triglycerides, high density lipoprotein cholesterol (HDL-C), c-reactive protein, insulin, and blood pressure (ii) cardiac function: global longitudinal strain (%), stroke volume (L) and ejection fraction (%), and (iii) mood and wellbeing.

5 STUDY DESIGN and METHODS of DATA COLLECTION AND DATA ANALYSIS

Study design

A repeated measures, randomised cross over study design will be used. All data collection will take place at the Sport and Exercise Science Laboratories, University of Bedfordshire, [name]. After a preliminary testing session, participants will complete three, 6-hour experimental conditions in a random order: 1) uninterrupted sitting; 2) sitting interrupted with standing breaks, and 3) sitting interrupted with light intensity stepping breaks. There will be a washout period of at least 72 hours between conditions, as previous research suggests that a single session of exercise can affect blood glucose levels for the following 48 hours (Mikines, et al., 1988). Participants will be randomised to order of condition using computer generated random numbers. This will assign them a trial order using block randomization with balanced block sizes. Participants will be blinded to the trial condition until they arrive on the day of their first and second experimental conditions.

Preliminary testing

Patients will first attend a preliminary testing session where they will become accustomed to light intensity stepping on the spot to the beat of a metronome and use of the Borg RPE scale. This will ensure patients are familiar with an intensity that is equivalent to an RPE of 8-11 (very light to light) that will be used in the respective experimental condition. Participants will step to different metronome paces starting at a slow pace and building up gradually every 1-2 minutes until an RPE of 8-11 is found. This imitates the intensity recommended within the warm up of CR, as recommended by BACPR. Height (cm) and weight (kg) will also be measured using a stadiometer (Harpenden 98.602, Holtain Ltd., Crymych) and digital scales

(Tanita BWB0800, Tanita Corp., Tokyo, Japan) respectively, to calculate body mass index (kg/m^2).

Experimental Protocol

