Each meal will provide approximately 30% of estimated daily energy requirements. This will be calculated for each individual participant using a prediction equation based on individual's height, weight and gender. Breakfast will consist of bran flakes, whole milk, and a honey and granola bar and will consist of 54% carbohydrate, 34% fat and 12% protein. Lunch will consist of a chicken sandwich, salted crisps and jammie dodger biscuit (54% carbohydrate, 34% fat and 12% protein). The macronutrient composition of the meals are in general agreement with guidelines recommended for a balanced diet (Public Health England, 2016). Participants will be encouraged to consume their meal within 15 minutes. The time taken will be recorded in the first condition and this time will then be replicated in the latter two conditions. Water will be available for the participants ad libitum during their first experimental condition visit. This volume of intake will be recorded and the same amount provided in the following two conditions spread over the day.

Data collection

Finger prick capillary whole blood samples will be collected at baseline, 30, 60, 120, 180, 210, 240, 300 and 360 minutes throughout the conditions to allow later analysis of glucose, triglycerides, HDL-C, and insulin. Blood samples will be taken after the hand is pre-warmed in warm water for approximately 5 minutes. Blood pressure and heart rate will be measured 5 minutes before each of the blood samples are taken. Cardiac function measures and mood and wellbeing will be measured at baseline and post-condition

[figure not shown]

Figure 1: Schematic of experimental protocol, PA, physical activity; ECG, electrocardiogram.

Biochemical analyses

600 μ l of whole capillary blood will be collected using EDTA microvette tubes that will be centrifuged (Heraeus Pico 17 microcentrifuge; Thermo Scientific, Loughborough, UK) at 2000 \times g for 5 min. The plasma will then be pipetted into 0.5 mL eppendorf tubes and stored at -80° for later analysis. Plasma glucose and triglyceride concentrations will be analysed via enzymatic colorimetric methods using a benchtop analyser (Pentra 400; HORIBA ABX Diagnostics, Montpellier, France). Plasma insulin concentrations will be determined using an enzyme linked immunosorbent assay technique (Mercodia, Uppsala Sweden).

Blood pressure and heart rate

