Blood pressure and heart rate will be measured in an upright, seated position using an automated device (Omron M5-1 automated oscillatory device, Omron Matsusaka Co. Ltd., Matsusaka, Japan). The same arm will be used for BP measurement each time throughout the study, which will be taken on the left arm unless there is preference for the right arm due to any potential previous medical conditions. A single measure will be taken at each time point apart from baseline where two measures will be taken with a 2 minute rest between each.

Cardiac function

In a laboratory, the patient will be asked to undress from the waist up and lay on the medical couch in the left lateral decubitus position. Here, a scanning gel will be applied to the echocardiogram probe. This forms part of the echocardiogram system; Vivid 7, GE Medical, Mius Ltd., Gloucester, UK). Parasternal and apical views will be acquired (Armstrong and Ryan., 2012). Once these images are collected and stored, the gel will be removed from the probe and chest. All images will be stored anonymously, where participants will be given a participant ID number. All image analysis will be completed using Echopac software (GE Healthcare, Version 113, GE healthcare, Chicago, Illinois, United States).

LV mass, LV mass index (adjusted for height), LV end diastolic volume, LV end systolic volume, wall motion score index (WMSI), E/A ratio, relative wall thickness, and deceleration time will be measured. These measures will be used to calculate left ventricular function.

Mood and wellbeing

The Positive and Negative Affect Scale (PANAS) questionnaire (Watson et al., 1988) will be used to assess current mood and subjective wellbeing measured using the National Wellbeing Measurement. These questionnaires will be completed at baseline and immediately after

cardiac function measures post-condition. There is a significant correlation post cardiac event and poor mental health (Chadda, et al., 2016). This questionnaire will therefore measure whether breaking up sitting time regularly within this population will improve mental health measures. PANAS is a valid questionnaire, which can be modified to measure changes in mood across a day, without losing its validity (Watson, et al., 1988). If incidental findings of anxiety or depression occur, the GP shall be informed via a letter sent directly to them.

Data analyses

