8.6 Data protection and patient confidentiality

All investigators and study site staff will comply with the requirements of the Data Protection Act 2018 with regards to the collection, storage, processing and disclosure of personal information and will uphold the Act's core principles, to ensure that patient confidentiality is maintained at all times.

Personal information on source documentation will be filed in a locked cabinet, with only the core research members allowed access. Upon registration to the study, participants will be given a unique participant ID number, which will henceforth be used in all data collection within the study. This will be determined using a number system (Move-01, etc.). A confidential log will be kept by the research team to identify participants with their anonymous ID numbers, which will be encrypted on a secure computer. All other electronic documentation will also be encrypted. Only direct members of the research team will have access to the data, and will be listed on the study's delegation log. Where data is transmitted to sponsors, if necessary, it will only be identifiable by its participant ID number, thus not becoming patient identifiable at any time.

Upon completion of the study, data will be stored for a minimum of 5 years. The data custodian for the Project is [name], Lecturer for Clinical Physiology.

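### Nothing in the protocol keeps the person who measures the stored echocardiograms unaware of condition; re-coding the files before measurement would close this gap for the non-primary cardiac outcomes

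*Protocol*

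**What the plan says.** Section 4.1 asks whether breaking up sitting "acutely improves cardiometabolic risk markers and cardiac function in individuals who have suffered a myocardial infarction". Section 4.2 names postprandial glucose as primary and lists, among the other outcomes, "cardiac function: global longitudinal strain (%), stroke volume (L) and ejection fraction".

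Section 5 sets out how the cardiac measures are obtained:

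- **Timing** (Data collection): "Cardiac function measures and mood and wellbeing will be measured at baseline and post-condition".
- **Storage** (Cardiac function): "All images will be stored anonymously, where participants will be given a participant ID number".
- **Measurement** (Cardiac function): "All image analysis will be completed using Echopac software". No role is given for this step and no masking is stated.
- **Allocation** (Study design): "Participants will be randomised to order of condition using computer generated random numbers".
- **Blinding** (Study design): "Participants will be blinded to the trial condition until they arrive on the day of their first and second experimental conditions". This is the only blinding statement in the protocol.

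Section 8.6, on data protection, explains the code: "participants will be given a unique participant ID number, which will henceforth be used in all data collection within the study". The Protocol Contributors section lists three roles. The student's role includes both conducting the study and analysing the data.

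**The concern.** Tracing borders and judging wall motion on an echocardiogram involve the reader's judgement, unlike a plasma glucose value from an analyser. Section 1 also argues that a benefit to cardiac function is plausible, so a reader who knows the condition may know the direction hoped for.

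In a cross-over, a reading habit that is the same under all three conditions cancels. A habit that shifts with the condition does not, and would appear as a condition effect. Participants and session staff cannot be masked to sitting, standing or stepping during the six hours. The measurement step can be masked, because the images are stored and read later. The protocol fixes how the images are coded, but the code it chooses protects identity and does not address condition.

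**Working it through.** **Step 1: does the stated coding mask condition?** The protocol has no figure to reproduce here, so the passages are set side by side.

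- The ID is one number per participant, used throughout (section 8.6). It is the same in all three conditions.
- Order is randomised per participant (section 5, Study design). The ID, or a visit label, therefore does not reveal the condition on its own.
- It can do so for someone who attended the session or holds the allocation list. No section says the reader did either, and no section prevents it.
- Conduct and data analysis sit in one role (Protocol Contributors). Data analysis there need not mean image measurement.

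Reading with condition known is therefore permitted but not shown.

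**Step 2: would an unmasked reading tendency matter?** The documents give no echo SD and no reading bias, so what follows is an illustration on assumed ratios only.

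Let *b* be the shift in the post-condition reading of one condition that remains after the baseline covariate, and SD the residual within-participant SD. With three conditions, the squared deviations of the condition means sum to *b*²(1 − 1/3) = (2/3)*b*². The overall F test has 2 and 2(*n* − 1) degrees of freedom, and its noncentrality is *n* × (2/3) × (*b*/SD)²:

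- *n* = 18: 12(*b*/SD)², df 2 and 34
- *n* = 23: 15.33(*b*/SD)², df 2 and 44

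False-positive rate at a nominal 5%:

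| Assumed *b*/SD | *n* = 18 | *n* = 23 |
|---|---|---|
| 0.1 | 5.8% | 6.1% |
| 0.2 | 8.5% | 9.6% |
| 0.4 | 20% | 25% |

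If the shift is equal in all conditions, the deviations are zero and the rate stays at 5%. A shift common to both scans of a visit would be partly removed by the baseline covariate, so *b* is only the part that survives. The table shows the mechanism, not the size of the problem in this trial.

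**Step 3: workload of re-coding.** Up to 23 participants × 3 conditions × 2 scans = 138 scan sets, or 18 × 3 × 2 = 108 if 18 complete. At an assumed 2 to 5 minutes each:

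- 138 sets: 276 to 690 minutes, or 4.6 to 11.5 hours
- 108 sets: 216 to 540 minutes, or 3.6 to 9 hours

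**The case against.** The strongest reply is that this is an omission, not an error. The Cardiac function text says nothing false, contradicts nothing and does not prescribe unmasked reading. That is correct, and it limits the weight of the point. It does not remove the point: masking of outcome readers is a matter of trial conduct, the protocol already covers both blinding and image handling, and the remedy is a concrete change in procedure.

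A second reply is that the reader may be identified somewhere not visible here. Names are removed from this copy, figures are not shown, and section 8.6 refers to a delegation log. This also stands, so the absence of a named reader is not held against the protocol. A log entry assigning the task would still not make the reader unaware of condition.

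A third reply is that any false-positive rate rests wholly on assumed inputs and runs from near nominal to clearly inflated. That stands too, and the rates should not be used to set priority.

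Two stronger readings are tempting and are not supported. A reader might infer that the echocardiograms *will* be read with condition known, because one role covers conduct and analysis; no section assigns image measurement to that role. A reader might also infer that the participant ID gives the condition away; because order is randomised per participant, it does so only when combined with other knowledge.

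**Conclusion.** The point holds as a modest design improvement. The protocol leaves open that strain, stroke volume and ejection fraction are measured with condition known, and it includes no safeguard against this although off-line measurement makes one available. Whether it would happen is not established, and the size of any resulting bias cannot be calculated from the documents.

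The effect is confined to the cardiac outcomes, which are non-primary but form part of the stated objective. Postprandial glucose, the alpha level and the sample size in section 7.2.1 are untouched. The conclusion assumes that no document outside this copy already requires masked reading. If one does, the protocol need only say so.

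**What to change.** Add to section 5, Cardiac function, text along these lines:

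> Before measurement in Echopac, a member of the existing team who does not measure the images will re-label the files with random codes that hide condition, participant ID, visit, scan date and, where possible, time point. Files will be measured in random order. The key will stay closed until all measurements are locked, except that the key-holder may identify a single file at any time so that the GP notification described in section 8.1 can proceed without delay.

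Hiding ID, visit and date belongs in the text itself, because together they could let a reader who attended sessions recall the condition. Hiding the time point is good practice but matters less for comparing conditions. The exception for single files is needed so that the locked key does not conflict with section 8.1.

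**Cost.** Some hours of re-labelling (4.6 to 11.5 for 138 scan sets under the assumed handling time) and a key-holder duty in a study with no external funder. No extra reader, scan or visit is needed. Three contributor roles are listed, so someone other than the reader exists, although their available time is not stated. Random-order measurement implies working in batches, so the reading timetable has to be reconciled with section 8.1 for anything first noticed at measurement. Acquisition remains unmasked, so the protection is partial. The text should be in place before any image is measured, since unmasked readings can be corrected only by re-reading.

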that breaking up sitting time with both standing and light physical activity have benefits on postprandial cardiometabolic risk markers (including blood pressure, glucose, insulin and triglycerides) (Henson et al., 2016; Dempsey et al., 2016). For instance, a study in dysglycaemic, overweight, postmenopausal women found that breaking up sitting time with 5 minutes of standing every 30 minutes resulted in a 34% reduction in postprandial glucose incremental area under the curve (iAUC). Breaking up sitting with 5 minutes of light-intensity self-paced walking (10-12 on the Borg Rating of Perceived Exertion [RPE] scale) every 30 minutes resulted in a 28% reduction in glucose iAUC. Similar effects were seen for insulin iAUC, which was reduced by 20% with standing breaks and 37% by light intensity walking breaks (Henson, et al., 2016). In patients with T2DM, improvements in postprandial cardiometabolic risk markers (glucose, insulin and triglycerides) were seen when sitting was interrupted with light intensity walking (3 minutes every 30 minutes) and simple resistance exercises (3 minutes every 30 minutes). Overall, there was a reduction in postprandial glucose iAUC of 39% in both conditions and postprandial insulin iAUC by 36% and 37% in the light-intensity walking condition and resistance activities conditions, respectively. Postprandial triglycerides were also significantly attenuated in the simple resistance activities condition, but not in response to light-intensity walking breaks. Light-intensity walking and resistance exercise breaks also resulted in a significant reduction in systolic and diastolic blood pressure (Dempsey, et al., 2016). To our knowledge, there have been no studies conducted to date evaluating the effects of breaking up prolonged sitting on cardiometabolic risk markers in cardiac patients.

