Statistical analyses will be conducted using SPSS Version 23 (IBM, Armonk, NY, USA). Postprandial glucose, insulin, triglycerides, HDL-C, SBP and DBP iAUC will be calculated for each condition using the trapezoidal rule. Mean arterial blood pressure will be calculated as:

$MAP \cong P_{\text{Diastolic blood pressure}} + \frac{1}{3} (P_{\text{systolic blood pressure}} - P_{\text{diastolic blood pressure}})$. Normality of the data will be checked using quantile-quantile plots. Linear mixed models will be used to compare the dependent variables between conditions. Fixed factors for each model will be condition and fasting outcome variable values (as covariates) and participants will be entered as a random factor. Post-hoc analyses will be conducted use the Sidak adjustment if a significant main effect of condition is present. Cohen's d effect sizes will be calculated to describe the magnitude of differences between conditions. Data will be presented as a mean (95% CI). Significance will be set at $p < 0.05$.

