7.2 Sampling

7.2.1 Size of sample

An estimated sample size was calculated using G* Power (version 3.1.9.4). Based on previous data (Bailey, et al., 2019), it was estimated that 18 participants would be needed to detect a medium effect size ($f=0.5$) difference in iAUC postprandial glucose between conditions with 95% power at an alpha level of 5% and within-person correlation of 0.5. To allow for 20% drop out, 23 participants will be recruited. If drop out occurs and recruitment is lower than 18, participants will be replaced to ensure minimum recruitment is met. This decision will be pragmatic in accordance with study timeline.

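### SBP and DBP are to be summarised as incremental AUC, which loses part of the effect if area below baseline is ignored and adds nothing if it is counted; a 6-hour time-averaged value is at least as good either way.

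*Protocol*

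**What the plan says.** Section 5, Data analyses, applies one summary measure to six outcomes: "Postprandial glucose, insulin, triglycerides, HDL-C, SBP and DBP iAUC will be calculated for each condition using the trapezoidal rule". The treatment of area below baseline is not given. The model already adjusts for the starting value: "Fixed factors for each model will be condition and fasting outcome variable values (as covariates) and participants will be entered as a random factor". Mean arterial pressure is calculated in the same paragraph but is not in the iAUC list.

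Blood is sampled on this schedule: "Finger prick capillary whole blood samples will be collected at baseline, 30, 60, 120, 180, 210, 240, 300 and 360 minutes". Blood pressure is taken 5 minutes before each sample. On the number of readings, section 5 says: "A single measure will be taken at each time point apart from baseline where two measures will be taken".

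On the expected direction, section 1 reports from a study in type 2 diabetes: "Light-intensity walking and resistance exercise breaks also resulted in a significant reduction in systolic and diastolic blood pressure". Section 3 hypothesises a general reduction in risk markers.

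On status, section 4.2 says: "The primary outcome of this study is postprandial glucose". Blood pressure and HDL-C are among the other outcome measures.

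**The concern.** Incremental AUC is built for a marker that starts low when fasting and climbs after a meal, as glucose, insulin and triglycerides do. The protocol describes no such rise for blood pressure, and the effect of interest is a reduction.

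Two versions of iAUC are in use. The positive-only version sets area below baseline to zero. The net version subtracts it. With the positive-only version, a visit whose pressure lies at or below its fasting value scores zero or close to it, and any further fall cannot be seen. The estimated difference between conditions then moves toward zero and power drops. Estimates matter here as well as tests, because the plan reports means with 95% confidence intervals and Cohen's d.

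**Working it through.** **Figure in the plan.** The protocol gives no power or effect size for blood pressure, so there is nothing to reproduce. Its 18 participants (section 7.2.1) were derived for glucose iAUC and serve here only as the number of completers.

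**Inputs from the protocol.** Times 0, 30, 60, 120, 180, 210, 240, 300 and 360 min; two averaged readings at baseline and one at each later time; fasting value as covariate; participant as random factor.

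**Assumed inputs, not in the protocol.** Between-participant SD 12, visit SD 4 and single-reading SD 6 mmHg; a constant true effect of -4 or -5 mmHg against sitting; sitting pressure shifted from baseline by a range of values.

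**1. Net iAUC adds nothing to the planned model.** With y0 the baseline value, net iAUC = total AUC - 360 × y0 (in minutes). If total AUC = a + b × condition + c × y0 + participant + error, then net iAUC = a + b × condition + (c - 360) × y0 + participant + error. The condition effect b, its standard error and its p-value are identical. Dividing total AUC by 360 only rescales b to mmHg.

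**2. Why positive-only iAUC loses information.** A later reading minus baseline has within-visit error SD √(6² + 6²/2) = √54 = 7.3 mmHg. Single readings therefore often lie below baseline even when the visit mean does not.

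Noise-free profiles with a -5 mmHg effect show the mechanism. The first 30-minute interval counts half, so the true AUC difference is -5 × (6 - 0.25) = -28.75 mmHg·h.

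| Sitting BP relative to baseline | Positive-only difference | Net difference |
|---|---|---|
| at least 5 mmHg above | -28.75 | -28.75 |
| at baseline | 0 | -28.75 |
| 5 mmHg below | 0 | -28.75 |

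**3. Simulation, -5 mmHg effect** (sitting against one break condition, 18 participants, 4,000 runs, baseline-adjusted):

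| Sitting shift (mmHg) | Positive-only estimate (mmHg·h) | Share of -28.75 lost | Power, positive-only | Power, net or total |
|---|---|---|---|---|
| +5 | -18.5 | 36% | 93% | 96% |
| 0 | -10.1 | 65% | 81% | 96% |
| -5 | -3.7 | 87% | 55% | 96% |
| -10 | -0.8 | 97% | 19% | 96% |

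The share lost is 1 - estimate/28.75; for example, 1 - 18.5/28.75 = 36%. Net and total AUC gave the same results in every scenario, between -28.6 and -28.9.

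**4. Simulation, -4 mmHg effect** (18 completers). Each power cell is positive-only against net or total AUC. Simulation A used 1,500 runs per scenario; B used three conditions.

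| Sitting shift (mmHg) | A: power | B: power | Active visits with positive-only iAUC exactly zero (A) |
|---|---|---|---|
| +4 | 82% v 88% | 84% v 89% | 6% |
| 0 | 71% v 89% | 79% v 92% | 21% |
| -4 | 53% v 87% | 48% v 92% | 46% |

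By step 1, net and total power cannot depend on the shift, so their spread within a column is simulation error. As a 6-hour mean the true difference is -4 × 5.75/6 = -3.83 mmHg. Positive-only iAUC divided by 6 h gave between -0.7 and -2.4 mmHg, that is 18% to 63% of it. With no true effect, all versions in A rejected in about 4% of runs, so the fault is lost effect and power, not false positives.

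**The case against.** The strongest reply is that the loss depends on a definition the protocol does not give. Section 5 does not say that area below baseline is discarded, a SAP that is not shown may define iAUC as net, and the tests are then unaffected. This stands, and it makes the power loss conditional. It does not remove the point. The protocol has fixed iAUC for blood pressure, and one replacement gives the same test under the net reading and a better one under the positive-only reading.

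A reader might infer that the protocol expects breaks to push blood pressure below its own baseline. The documents do not support this. The cited reduction comes in a paragraph comparing interrupted with uninterrupted sitting, and no fasting reference is given. If sitting pressure rises and breaks blunt the rise, the loss of power is small: 3 to 6 points in the simulations with sitting 4 or 5 mmHg above baseline. The estimate still shrinks by about a third in those cases, because single readings scatter below baseline.

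A reader might also extend the argument to HDL-C, which is in the same list. The protocol predicts no fall in HDL-C and treats low values as adverse, so the blood pressure argument does not carry over.

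Finally, all the SDs and effects are assumed, and nothing in the protocol says where sitting pressure will lie. The figures show a range and are not a forecast for this trial.

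**Conclusion.** The point holds in conditional form. For SBP and DBP, iAUC is either harmful (positive-only) or redundant (net), and in neither case does it improve on the time-averaged value.

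If it is positive-only, and under the assumed SDs of 12, 4 and 6 mmHg with a -4 mmHg effect and 18 completers, power falls from about 90% to roughly 50-85% and the estimate to between about one fifth and three fifths of its true size. If it is net, inference is unchanged and only the scale (pressure × time above baseline) is harder to read than mmHg.

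It would go too far to say that the planned blood pressure tests are underpowered as written, since the version of iAUC is not stated. The primary outcome, postprandial glucose, is not touched, nor is the use of iAUC for insulin and triglycerides. The change is worth making because it is cheap, and because a choice between the two versions after seeing the data could alter the blood pressure conclusion.

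**What to change.** In section 5, Data analyses, take SBP and DBP out of the iAUC list and add a sentence to this effect: SBP and DBP (and MAP, if analysed) will be summarised for each condition as the 6-hour time-averaged value, that is total trapezoidal AUC divided by 360 min, and compared with the same mixed model and fasting-value covariate. Keep iAUC for glucose, insulin and triglycerides. HDL-C may use the time-averaged value for consistency, but no loss is claimed there.

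The cost is one sentence, agreed before the data are seen. No new data or visits are needed. If net iAUC was intended, the blood pressure p-values do not change and the estimates are simply expressed in mmHg.

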7 SAMPLE AND RECRUITMENT

7.1 Eligibility Criteria

7.1.1 Inclusion criteria

- Patients post myocardial infarction (ST wave elevated MI or Non-ST wave elevated MI) within the past three months (confirmed by elevated blood biomarkers or electrocardiographic changes), in which the procedure/ recovery uncomplicated and are therefore classified as low risk.
- Aged 40 years or above.
- Any ethnicity.
- Individuals with diet controlled type 2 diabetes mellitus

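### The cross-over model has no visit (period) term although the order of conditions is randomised; a real visit trend would widen the confidence intervals and cost power

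*Protocol*

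**What the plan says.** The design is a three-condition, three-visit cross-over: "participants will complete three, 6-hour experimental conditions in a random order" (Protocol, section 5, Study design). Allocation is to order: "Participants will be randomised to order of condition using computer generated random numbers". It is blocked: "This will assign them a trial order using block randomization with balanced block sizes". The set of orders and the block size are not given.

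The analysis model is stated term by term (section 5, Data analyses): "Fixed factors for each model will be condition and fasting outcome variable values (as covariates) and participants will be entered as a random factor". The protocol does not mention a period, visit, order or sequence term, or any check for a visit effect. Because the sentence lists the terms for every model, this is a model the protocol has chosen and not a detail left for a later document.

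Three further passages bear on whether visits may differ. The gap between visits has a lower limit only: "There will be a washout period of at least 72 hours between conditions". Concealment covers two of the three visits: "Participants will be blinded to the trial condition until they arrive on the day of their first and second experimental conditions". Participants had their infarction "within the past three months" (section 7.1.1).

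**The concern.** A cross-over that balances conditions over visits is normally analysed with visit in the model. Balance keeps an average visit effect out of the condition comparison, but only a visit term takes it out of the residual. Without the term, the standard errors include variation that the design has already removed from the estimates. The intervals are then too wide and the tests conservative. After dropout the orders are no longer exactly balanced, and a small part of the trend also adds noise to the condition contrast.

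The protocol gives some reason to expect differences between visits. Participants are early in recovery, and the time spanned by the three visits has no upper limit. Water is freely available and eating time is observed at the first visit, then both are copied at the later ones. The third condition can be deduced by elimination. The 72-hour washout deals with carry-over of exercise effects, not with a trend over visits. The fasting covariate removes drift in the fasting value, not drift in the response to the meal.

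What is at stake is precision and power in a trial with 18 evaluable participants, not the validity of its conclusions.

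**Working it through.** **Inputs from the protocol.** Three conditions over three visits in blocked order (section 5). 18 evaluable and 23 recruited, f = 0.5, 95% power, alpha 5%, within-person correlation 0.5 (section 7.2.1).

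**Assumed, not in the protocol.** A linear trend D from first to last visit, in within-person SD, shown over a range; and sphericity.

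**1. The plan's own figure.** For the repeated-measures F test, lambda = f² × n × m / (1 − rho).

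- f = 0.5, n = 18, m = 3: lambda = 0.25 × 18 × 3 / 0.5 = 27 on 2 and 34 df; power 99.6%.
- With these inputs 95% power is reached at n = 12 (95.2%), so 18 is not reproduced.
- f = 0.4, n = 18: lambda = 0.16 × 18 × 3 / 0.5 = 17.28; power 95.4%.
- Dropout: 18 / (1 − 0.20) = 22.5, so 23 is reproduced.

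The mismatch on 18 is a separate matter. It is used here only as a reason to show power at f = 0.4 as well as at f = 0.5.

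**2. Exactly balanced orders.** Let the visit effects be −D/2, 0, +D/2. Each participant contributes D²/2 to the sum of squares. Without a visit term this falls into the residual:

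residual mean square = 1 + n(D²/2) / [2(n − 1)]

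For n = 18 and D = 1: 1 + 18 × 0.5 / 34 = 1.265, and its square root is 1.125. Multiplying by t(0.975; 34 df) / t(0.975; 32 df) gives a CI-width ratio of 1.122. The ratio is also 1.122 for n = 23.

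**3. With dropout, by simulation.** 10,000 trials per setting: 23 participants randomised in blocks over six orders, 18 kept at random, within-participant least squares with condition and a fasting covariate unrelated to the outcome, with and without two visit indicators.

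| Trend D (SD) | CI ratio, balanced (step 2) | CI ratio, 18 of 23 | Coverage without visit | Type I error of main effect, without / with visit |
|---|---|---|---|---|
| 0.25 | 1.006 | 1.00 | 95% | not computed |
| 0.5 | 1.030 | 1.02 | 95.5% | 4.7% / 5.3% |
| 1.0 | 1.122 | 1.11 | 96.5% | 3.1% / 4.9% |
| 1.5 | 1.260 | 1.25 | 97.7% | 1.9% / 5.3% |

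With no trend the 18-of-23 ratio is 0.99, so adding visit then costs about 1% in width.

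**4. Power at D = 1.** With correlation 0.5, the SD of the condition means is f / √(1 − 0.5) within-person SD. For f = 0.5 this is 0.707, giving means of −0.866, 0, 0.866 (evenly spaced) or 0, 0, 1.5 (one condition differs). For f = 0.4 the means are −0.693, 0, 0.693 or 0, 0, 1.2. The Sidak result is for the largest contrast and counts only if the main effect is significant, as the protocol specifies.

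| Effect | Test | Without visit | With visit |
|---|---|---|---|
| f = 0.5 | Main effect | 98.4–98.6% | 99.4–99.5% |
| f = 0.5, evenly spaced | Sidak | 98.2% | 99.3% |
| f = 0.5, one differs | Sidak | 93.8% | 96.8% |
| f = 0.4 | Main effect | about 90% | about 94% |
| f = 0.4, evenly spaced | Sidak | 87.7% | 93.0% |
| f = 0.4, one differs | Sidak | 75.0% | 83.0% |
| One differs by 0.9 SD (not a protocol value) | Main effect | 64.7% | 74.7% |

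With no trend, adding visit costs 0 to 1.3 points of power.

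**5. Sensitivity of the CI ratio at D = 1.** It is 1.16 if the whole shift falls between visits 1 and 2, 1.08–1.09 if orders were not blocked, 1.08 if the fasting covariate also carries the trend, and 1.09 if trends vary between participants around an average of 1 SD.

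**The case against.** The strongest reply is that nothing in the protocol shows a visit trend exists, and that 1 SD would be large. At f = 0.5 the largest difference between conditions is 1.5 to 1.73 within-person SD, so a 1 SD trend equals 58% to 67% of the hypothesised effect. The procedures also work against a trend: familiarisation before the first visit, an exercise ban, an overnight fast, a rest period, identical meals, and water and eating time copied from visit 1. The primary outcome is an incremental area and is also adjusted for the fasting value, so drift in glucose level is largely dealt with. At the protocol's effect size the main-effect loss is about one point, and power stays above the stated 95% either way. Finally, if recovery over unequal gaps drives the drift, a common visit term removes only its average part.

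Most of this stands, and it limits the size of the point. The trend is an assumption, up to 0.5 SD the loss is 2% to 3% of interval width at most, and no bias or false-positive risk follows. It does not remove the case for the term. The controls reduce visit effects without excluding them, and drift in the post-meal response is untouched by the baseline adjustment. The same model also serves blood pressure and the other outcomes. The size of a trend cannot be known beforehand, and adding the term after seeing the data would be a post hoc choice.

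**Conclusion.** The point holds as a matter of efficiency. The protocol specifies a cross-over model without visit, and no other passage supplies it. If visits differ materially, the intervals will be wider than they need to be: about 11% at an assumed trend of 1 within-person SD with 18 of 23 completing (12% with exact balance). At that trend, 18 participants give the precision of about 14 (18 / 1.122² = 14.3). The power loss is about one point on the main effect at f = 0.5, about four points at f = 0.4, and five to eight points on the largest Sidak contrast at f = 0.4.

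These figures rest on the assumed trend, on blocked orders and on random dropout. Below about 0.25 SD the omission makes no practical difference, and with no trend at all the model as written is very slightly better. The change is worth making because the possible loss is much larger than the cost of guarding against it.

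**What to change.** Replace the model sentence in section 5 (Data analyses) with:

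> Fixed effects will be condition, period (visit 1, 2 or 3, categorical) and the fasting value of the outcome; participant will be a random effect.

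Apply it to the glucose iAUC and to every other outcome, and make the change before any outcome data are examined.

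The cost is one extra term in SPSS and 2 error degrees of freedom. With 18 completers and the fasting value in the model there are 54 − 18 − 2 − 1 = 33, which become 31. Visit number follows from the randomised order, so nothing new has to be measured.
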